Ototoxicity and nephrotoxicity are the most common side effects associated with gentamicin therapy. Both effects are related to renal impairment and their frequency following a single dose of gentamicin is not known.

There have been rare reports of changes in electrolyte balance including hypocalcaemia and hypokalaemia caused by renal tubular dysfunction. Vestibular damage and ototoxicity may occur. This is usually reversible if observed promptly and the dose adjusted. Other adverse reactions associated with gentamicin therapy include nausea, vomiting, urticaria, reversible granulocytopenia, allergic contact sensitisation and neuromuscular blockade. There have been a few reports of anaphylactic reactions associated with gentamicin containing therapy.

Gentamicin 240mg will be given as a single intramuscular injection. In the published observational and controlled studies (including the three quoted in the Kirkcaldy systematic review[23]), 240mg was the most commonly chosen dose of gentamicin used (range 160mg-350mg) and no significant dose response effect is evident comparing across studies. Gentamicin has been used to treat gonorrhoea in Malawi for 20 years. A single 240mg i.m. dose was adopted there in 1993 as empirical therapy. In 2007 a survey confirmed continued susceptibility with all isolates having gentamicin MIC values of under 8 mg/l[24]. Slightly higher gentamicin MICs have recently been reported from a multinational European survey (MIC range 1 mg/l to 16 mg/l; modal MIC 8mg/l)[25].

The trial will be conducted in compliance with the protocol, GCP, ethics committee and MHRA requirements.

Gentamicin will be compared to ceftriaxone for the treatment of gonorrhoea. Participants will be randomised to receive either a single intramuscular injection of gentamicin (240mg) OR a single intramuscular injection of ceftriaxone (500mg). Additionally both groups will receive a single oral dose of azithromycin (1g).

The trial will recruit patients aged 16-70 years with a diagnosis of genital, pharyngeal and/or rectal gonorrhoea attending a participating sexual health clinic in the United Kingdom.

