2.2 Secondary Objectives

Secondary objectives of the study are:

- To determine whether a single intramuscular dose of gentamicin is safe and well tolerated
- To determine whether a single intramuscular dose of gentamicin is cost effective to the NHS when used to treat gonorrhoea
- To determine the relationship between clinical effectiveness and the laboratory measurement of antibiotic effectiveness (the minimum inhibitory concentration (MIC) required to inhibit growth of *N. gonorrhoeae*)

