4.4 Primary and Secondary Outcome Measures

Primary outcome measure.

The primary outcome measure is clearance of *N. gonorrhoeae* at all infected sites confirmed by a negative NAAT, two weeks post treatment (as recommended by the British Association for Sexual Health and HIV). The results from the AC NAAT will be considered primary.

Secondary outcome measures

Secondary outcomes are

- clinical resolution of symptoms
- frequency of nausea/vomiting, hearing loss, dizziness and rash.
- frequency of other adverse events
- tolerability of therapy
- relationship between clinical effectiveness and MIC to inhibit N. gonorrhoeae growth
- cost effectiveness

The NAAT is an automated laboratory test and therefore it is not subject to bias through knowledge of treatment allocation. The method of NAAT performed varies between centres, therefore for those centres where the AC NAAT method is not used by the local laboratory, additional swabs will be taken and sent for testing at a central laboratory using this method. This will ensure consistency in diagnosis and response for all participants for the ascertaining the primary end point of the study.

A doctor/nurse independent of the trial will administer the study drug and will therefore not be blinded to the treatment allocation. The participant and the physicians/nurses performing the initial and follow up assessment 2 weeks after treatment, and the laboratory staff performing microbiology analyses will be blinded to the treatment given in order to minimise any bias in the collection of outcome data.

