14.1 Sample size

Based on an efficacy rate of 96% for the ceftriaxone regimen which is consistent with previous trials, a total sample size of 646 for analysis (323 in each group) will achieve 90% power to detect non-inferiority with lower confidence limit for the absolute risk difference of 5%. The significance level is 0.025. To allow for a loss to follow-up rate of up to 10%, the study will recruit a total of 720 participants. A 5% lower confidence interval was acceptable to 17 of 24 sexual health patients whose opinion was sought, and provides a realistic recruitment target.

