14.2 Statistical Analysis

Continuous variables will be summarised in terms of the mean, standard deviation, median, lower and upper quartiles, minimum, maximum and number of observations. Categorical variables will be summarised in terms of frequency counts and percentages. Descriptive statistics of demographic and clinical measures will be used to compare balance between the randomised arms at baseline.

The primary approach to between-group comparative analyses will be by intention-to-treat without imputation of missing outcome data. Sensitivity analyses will be conducted to investigate the impact of missing primary outcome data, using simple and multiple imputation. Due to both interventions being single dose administered immediately following randomisation, non-adherence with treatment allocation is expected to be negligible. Therefore additional sensitivity analyses that aim to estimate treatment effect among those who have adhered with allocation are not expected to be required.

The evaluation of the primary clinical outcome variable will be performed using a general linear model for binary outcome adjusted by clinic site. The primary efficacy parameter

comparing gentamicin with ceftriaxone will be the risk difference in the proportion of participants clear of infection at two weeks follow up along with the 95% confidence interval. Gentamicin will be regarded as non-inferior if the lower 95% confidence limit for the risk difference in confirmed clearance is -5 percentage points or greater.

Secondary outcomes will be similarly analysed using appropriate regression models dependent on data type (binary, continuous etc), adjusted for clinic site and baseline value of the outcome variable if collected.

We are interested in whether treatment efficacy differs by site of infection. Participants may have infection at multiple sites, and up to seven different combinations of 1/2/3 sites are possible. For each of the three infection sites, we will separately estimate clearance by treatment arm along with 95% confidence intervals, rather than formally fit an interaction term for different combinations of infection site in the regression model. Any suggestion of a differential effect according to infected site would require confirmation in future research.

Safety and tolerability analysis will be of descriptive nature. Frequency counts and percentages of the per-specified main categories of side effects and AEs will be presented by treatment arm.

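### Section 14.2 gives two overlapping rules for the safety outcomes, and the descriptive one leaves the safety objective without a between-arm difference or interval

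*Protocol*

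**What the plan says.** Protocol section 2.2 sets a secondary objective: "To determine whether a single intramuscular dose of gentamicin is safe and well tolerated". Section 4.4 lists six secondary outcomes. Three concern safety: "frequency of nausea/vomiting, hearing loss, dizziness and rash", other adverse events, and tolerability of therapy. Section 12.2.1 names the pre-specified events as nausea, vomiting, hearing problems, dizziness and rash, collected by targeted questioning at the two-week visit.

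Section 14.2 then gives two instructions. The first is general: "Secondary outcomes will be similarly analysed using appropriate regression models dependent on data type (binary, continuous etc), adjusted for clinic site" (and for baseline value if collected). The second comes at the end of the section: "Safety and tolerability analysis will be of descriptive nature". It continues: "Frequency counts and percentages of the per-specified main categories of side effects and AEs will be presented by treatment arm". The statistical methods part of the synopsis repeats both. Neither place says that the second instruction is an exception to the first.

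**The concern.** Three of the six secondary outcomes fall under both instructions. Two statisticians could each follow section 14.2 faithfully and produce different outputs: a site-adjusted comparison of the arms, or a table with no comparison. A later analysis plan would have to set aside one of the two sentences, so this is more than detail left for that plan to fill in.

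The descriptive rule also fits the objective poorly. Section 2.2 asks a whether-question about safety in a randomised trial with a concurrent comparator, in which both arms also receive azithromycin. The difference between arms separates what gentamicin adds, relative to ceftriaxone, from background complaints and from the shared azithromycin. Section 14.2 commits to 95% confidence intervals for the primary outcome and for clearance by infection site and arm, but to none for the named harms. Section 1 says of ototoxicity and nephrotoxicity that "their frequency following a single dose of gentamicin is not known", so the reader has little outside knowledge against which to judge small counts. What is at stake is whether the report shows how much excess the data cannot rule out.

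**Working it through.** **Which outcomes fall under which rule**

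| Secondary outcome (4.4) | Regression rule (14.2) | Descriptive rule (14.2) |
|---|---|---|
| Clinical resolution of symptoms | yes | no |
| Named side effects | yes | yes |
| Other adverse events | yes | yes |
| Tolerability | yes | yes |
| Effectiveness against MIC | yes | no |
| Cost effectiveness | yes as worded (section 17 has its own plan) | no |

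The overlap is rows two to four.

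**The plan's own sample size**

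The protocol states no figure for safety, so the denominator comes from section 14.1: "Based on an efficacy rate of 96% for the ceftriaxone regimen", a 5-point margin, significance level 0.025 (taken as one-sided) and 90% power.

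- n per arm = (1.960 + 1.282)² × 2 × 0.96 × 0.04 / 0.05² ≈ 322.8, so 323 per arm and 646 in total. Power at 323 is 90.0%.
- Allowing for 10% loss: 646 / 0.90 ≈ 717.8, so 718, against 720 stated.

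The sizing reproduces and is not in question. It concerns clearance only. Side effects are collected at the same two-week visit, so 323 per arm is a reasonable denominator for them too.

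**What 323 per arm can exclude (event counts assumed)**

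*No events in one arm.* The exact upper limit (one-sided 97.5%) is 1 − 0.025^(1/323) = 0.01136, or 1.1%. If all 360 randomised to the arm returned, it would be 1 − 0.025^(1/360) = 0.0102, or 1.0%.

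*Three events in each arm.* Take p = 3/323 = 0.00929 and z = 1.96. The Wilson limits for one arm are

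[p + z²/2n ± z√(p(1 − p)/n + z²/4n²)] / (1 + z²/n),

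which gives 0.00316 to 0.02695. The Newcombe upper limit for the difference is

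0 + √[(0.02695 − 0.00929)² + (0.00929 − 0.00316)²] = 0.0187, or 1.9 points.

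The same method for other assumed counts:

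| Gentamicin vs ceftriaxone events | Difference (points) | 95% CI (points) |
|---|---|---|
| 0 vs 0 | 0 | −1.2 to 1.2 |
| 3 vs 3 | 0 | −1.9 to 1.9 |
| 6 vs 3 | 0.9 | −1.1 to 3.2 |
| 6 vs 6 | 0 | −2.4 to 2.4 |
| 16 vs 16 | 0 | −3.5 to 3.5 |
| 32 vs 32 | 0 | −4.7 to 4.7 |

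With three events in each arm, both rates are about 0.9%, and the interval reaches an excess of twice that size. Power figures for a significance test are not used here, because neither the descriptive rule nor the proposed change involves a test.

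**The case against.** The strongest reply is that a specific sentence normally qualifies a general one: safety items are descriptive and the rest are modelled. That is a fair reading and probably the intended one, so this is an unreconciled overlap more than a flat contradiction. It still has to be inferred, because no exception is written in 14.2 or the synopsis.

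Second, descriptive safety reporting is common in a trial sized for efficacy. Section 14 promises a full analysis plan, which could add intervals, and the word descriptive does not forbid them. This stands in part: a missing interval would not by itself be an error. The overlap is in the protocol's own text, however, and the outputs it names stop at counts and percentages.

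Third, a reader can compute an interval from the published counts. That is true, and it means no information is lost; it also shows how little the change asks.

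Fourth, safety oversight does not rest on one table. The data monitoring committee can see unblinded safety data and reviews all serious adverse events, and causality is assessed for every event. This stands, but it concerns monitoring, not how the section 2.2 objective is reported.

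Three stronger readings are tempting and unsupported. A reader might infer that the plan relies on bare counts, but it specifies percentages by arm as well. A reader might infer that similar percentages will be taken to show safety. The protocol states no such rule, and its objective asks whether gentamicin is safe without presuming that it is. A reader might also infer from section 1 that the trial is meant to supply the missing toxicity frequency. The protocol does not say so, and such a frequency would be a single-arm proportion, which 14.2 does report.

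**Conclusion.** The point holds in a limited form. Section 14.2 gives two rules for three of the six secondary outcomes and does not say which governs. Under the descriptive rule, the protocol names no between-arm estimate or interval for the pre-specified side effects that bear on the safety objective. The size is modest but not trivial: at 323 per arm, identical counts leave a possible excess of about 1.2 points (no events) to 4.7 points (32 events per arm), with 1.9 points at three events each. No events in an arm leaves a possible rate of about 1.1%. These figures rest on assumed counts and on the planned number being followed up.

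The evidence does not support a decision rule that calls gentamicin safe when an upper limit falls below some value. The only margin in the protocol is the 5 points for clearance, and none is given for harms. The primary analysis and the sample size are unaffected.

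**What to change.** In section 14.2, and in the matching synopsis text, make three changes:

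- State for each secondary outcome in 4.4 whether it is modelled or described, so that the named side effects, other adverse events and tolerability each have one rule.
- For nausea, vomiting, hearing problems, dizziness and rash, report the gentamicin minus ceftriaxone risk difference with a 95% confidence interval, using a score or exact method where counts are sparse. Keep counts and percentages for other adverse events.
- Say that the safety objective will be interpreted with these intervals in view, without a pass or fail threshold.

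If the sponsor prefers to stay purely descriptive, the alternative is to reword the section 2.2 objective so that it undertakes to describe safety and tolerability, and to write the exception into 14.2.

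The cost is a few sentences and slightly more analysis. No new data, visits or participants are needed. The downside is that the safety statement may read less reassuringly, because the intervals will show what a trial of this size cannot exclude.

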15 DATA HANDLING AND RECORD KEEPING

15.1 Data Handling and Record Keeping

Each participant will be assigned a trial identity code number, allocated at randomisation, for use on eCRFs, other trial documents and the electronic database. The documents and database will also use their initials (of first and last names separated by a hyphen or a middle name initial when available) and date of birth (dd/mmm/yyyy).

eCRFs will be treated as confidential and held securely in accordance with regulations. The investigator will make a separate confidential record of the participant's name, date of birth, local hospital number or NHS number, and Participant Trial Number (the Trial Recruitment Log), to permit identification of all participants enrolled in the trial, in accordance with regulatory requirements and for follow-up as required.

eCRFs shall be restricted to those personnel approved by the Chief or local Principal Investigator and recorded on the 'Trial Delegation Log.'

The Principal Investigator or designee shall electronically complete a declaration ensuring accuracy of data recorded in the eCRF.

Details about data handling will be specified in the Data Management Plan (DMP). This will include the agreed validation specification which will validate data for consistency and integrity as it is entered. Additional manual and electronic reviews may also be conducted and data queries may arise from such reviews.

Data will be held on clinical trial dedicated servers. These servers are located within a managed data centre that is managed/monitored 24/7. Security is both physical (secure limited access) and electronic (behind firewalls, access via user accounts (user name and password), restricted access – e.g. site user only have access to their sites data, and by user type/role). All access and data transactions are logged in a full audit trail.

Participants data are frozen on an ongoing basis once they are deemed to have a complete set of data that has passed data validation checks (i.e. there are no data queries outstanding). Once all participant data have been frozen, the trial database is locked (set to read only). This is done prior to the final analysis.

15.2 Direct Access to Source Data/Documentation

Source documents shall be filed at the investigator's site and may include but are not limited to, consent forms, current medical records, laboratory results and pharmacy records. Only trial staff as listed on the Delegation Log shall have access to trial documentation other than the regulatory requirements listed below.

The eCRF and all source documents, including progress notes and copies of laboratory and medical test results shall made be available at all times for review by the Chief Investigator, Sponsor's designee and inspection by relevant regulatory authorities (MHRA).

16 TRIAL ORGANISATIONAL STRUCTURE

16.1 Sponsor

The trial is sponsored by University Hospitals Birmingham NHS Trust.

16.2 Coordinating Centre

The trial is co-ordinated by the Nottingham Clinical Trials Unit (NCTU).

16.3 Trial Management Group (TMG)

The Trial Management Group (TMG) will be responsible for day-to-day management of the trial. Membership includes the CI, the Trial Manager and at least one other member of the NCTU. The TMG will be responsible for ensuring project milestones are achieved. The TMG will meet regularly throughout the duration of the trial.

16.4 Trial Steering Committee (TSC)

A Trial Steering Committee (TSC) has been established which includes an independent chair, independent and non-independent members and patient representatives. A minimum of 75% of the members will be independent. The TSC will meet to discuss and agree the protocol, and it will approve the Statistical Analysis Plan before the trial data are unblinded.

16.5 Data Monitoring Committee (DMC)

An independent Data Monitoring Committee (DMC) will be established and will operate in accordance with a trial specific Charter agreed with the TSC. It will be fully independent and will consist of a chair, expert statistician and a minimum of one independent clinician. They will have access to unblinded data if necessary. The DMC will review all Serious Adverse Events.

17 HEALTH ECONOMICS

The economic analysis will compare the costs associated with the current standard treatment, ceftriaxone, with those of the proposed alternative treatment, gentamicin, in the treatment of gonorrhoea. Given that the primary objective of the trial is to determine non-inferiority of gentamicin, the economic analysis will focus on establishing whether the use of gentamicin rather than ceftriaxone is cost-neutral in the treatment of gonorrhoea. This will involve the examination of costs and resource use to determine whether there are any differences between the two treatments.

The economic evaluation will adopt the perspective of the health service (NHS), and data on resource use and costs will be collected prospectively within the study. Resource use data will be collected via a nurse / assessor completed form and will include questions on drug use, GP or other clinic visits etc. For a small random subset of patients in both arms of the trial we will collect information on the length of consultation required for delivery of the treatment therapy. This will be for the purpose of validation only, to confirm that the delivery of the treatment and length of consultation is not relevant to the drug being administered. Unit cost estimates will be applied to resource use data to generate individual level cost estimates. The sources of unit costs will include routine or published literature (e.g. PSSRU Unit costs of Health and Social Care).

The results will be reported in terms of the cost per patient successfully treated (measured in terms of microbial clearance of *Neisseria gonorrhoeae*). We will carry out a range of sensitivity analyses to explore the robustness of these results to plausible variations in key assumptions, and to consider the broader issue of the generalisability of the results.

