8.3 Description of Study IMP(s)

All treatments will use standard clinic stock. Any licensed brand may be used.

Gentamicin injection (gentamicin sulphate Ph Eur equivalent to 80mg/2ml Gentamicin base).

Ceftriaxone powder for solution for injection.

Azithromycin and the lidocaine used in the preparation of the ceftriaxone injection are not considered to be IMPs.

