8.4 Preparation, Dosage and Administration

Participants will be randomised to receive either a single intramuscular injection (IM) of gentamicin (240mg) OR single IM injection of ceftriaxone (500mg). Additionally both groups will receive a single oral dose of azithromycin (1g).

The injections will be prepared, following the instructions in the relevant Summary of Product Characteristics (SMPC) by an unblinded nurse.

Ceftriaxone should be dissolved in 1% Lidocaine Injection BP according to the SMPC. The solution should be administered by deep intramuscular injection.

Gentamicin should be administered by deep intramuscular injection according to the SMPC.

Treatment should be given in clinic as soon as possible after randomisation.

The batch number(s) and manufacturer(s) of all the products administered and the date of administration should be recorded on the form provided through the electronic randomisation system.

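### Section 17 uses consultation times from a small subset only to confirm that delivery does not depend on the drug; the difference should be estimated and carried into the cost comparison

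*Protocol*

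**What the plan says.** Protocol section 17 puts the economic question in terms of neutrality: "the economic analysis will focus on establishing whether the use of gentamicin rather than ceftriaxone is cost-neutral in the treatment of gonorrhoea". It will answer this by "examination of costs and resource use to determine whether there are any differences between the two treatments". Resource use comes from a form completed by a nurse or assessor, which "will include questions on drug use, GP or other clinic visits etc". Delivery time is not among the named items.

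Delivery is handled separately: "For a small random subset of patients in both arms of the trial we will collect information on the length of consultation" needed to deliver treatment. The use of these times is then limited: "This will be for the purpose of validation only", namely "to confirm that the delivery of the treatment and length of consultation is not relevant to the drug being administered". The section does not say what follows if the times differ. It does promise a range of sensitivity analyses on key assumptions, without naming delivery time.

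Sections 8.3 and 8.4 describe different preparation for the two drugs. For the control arm, a powder has to be made up: "Ceftriaxone should be dissolved in 1% Lidocaine Injection BP according to the SMPC". The test drug is supplied as a solution: "Gentamicin injection (gentamicin sulphate Ph Eur equivalent to 80mg/2ml Gentamicin base"). Sections 7.2.1 and 8.6 require preparation out of sight of the participant and of blinded staff.

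**The concern.** The sentence fixes both the conclusion and the use of the data in advance. The conclusion is that delivery is unrelated to the drug, and the data serve only to support it. Not seeing a difference in a small sample is weak evidence that none exists. For clearance the protocol applies a stricter standard: section 14.2 requires a confidence limit to clear a stated bound before gentamicin is called non-inferior.

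Staff time to deliver the injection arises for every treated participant and may depend on the allocated drug. The documents give a concrete reason to estimate it rather than presume it equal, because one product must be reconstituted and the other must be drawn up from a solution. Cost-effectiveness is a stated secondary objective (section 2.2) and outcome (section 4.4). What is at stake is whether a finding of cost-neutrality would rest partly on an assumption that the trial collected data on but did not carry through.

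**Working it through.** **Figures in the plan.** The protocol gives no size, SD, power or tolerated difference for the timing subset, so there is no plan figure to reproduce on this point. Its only sample size is for the primary outcome (section 14.1), and that reproduces: n per arm = (1.960 + 1.282)² × 2 × 0.96 × 0.04 / 0.05² ≈ 323, or 646 in total. It has no bearing on the subset.

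**Inputs.** From the protocol: a small random subset in both arms, used for validation only (section 17); 240 mg gentamicin from an 80 mg/2 ml solution (sections 8.1 and 8.3); ceftriaxone powder dissolved in lidocaine (sections 8.3 and 8.4). Assumed here: subset sizes of 15 to 64 per arm, true differences of 0.5 and 0.8 SD, and a two-sided 5% comparison of means. The protocol specifies no test. The test serves only to show what a subset of a given size can distinguish.

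**Preparation.** 240 / 80 × 2 ml = 6 ml of gentamicin solution to draw up, against a ceftriaxone powder to dissolve. The steps differ, but the text does not show which takes longer.

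**Power.** The normal approximation is Φ(d√(n/2) − 1.96), with d in SD units and n per arm.

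- d = 0.5, n = 20: 0.5 × √10 = 1.581; 1.581 − 1.96 = −0.379; Φ = 0.35.
- d = 0.8, n = 20: 0.8 × √10 = 2.530; 2.530 − 1.96 = 0.570; Φ = 0.72.

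The exact t-test gives slightly lower values:

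| n per arm | Power, 0.5 SD | Power, 0.8 SD | 95% CI half-width (SD) |
|---|---|---|---|
| 15 | 26% | 56% | 0.75 |
| 20 | 34% | 69% | 0.64 |
| 30 | 48% | 86% | 0.52 |
| 50 | 70% | 98% | 0.40 |
| 64 | 80% | 99% | 0.35 |

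The half-width is t(0.975, 2n − 2) × √(2/n). At 20 per arm an observed difference of zero would still be compatible with differences up to 0.64 SD either way.

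**In minutes, by assumption.** With an SD of 5 minutes and 20 per arm, the half-width is 1.96 × 5 × √(2/20) = 3.1 minutes (normal approximation). Power is 24% for a true difference of 2 minutes, 48% for 3 minutes and 89% for 5 minutes. With an SD of 3 minutes the half-width falls to 1.9 minutes, and with 8 minutes it rises to 5.0.

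**The text against its own aim.** Section 17 wants to know whether the two treatments differ in cost. The same section collects a cost-relevant time in both arms and then restricts it to validation. The two statements are hard to reconcile unless the observed difference is allowed into the comparison.

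**The case against.** Much can be said for the section as written. Subset size, margin and method of analysis are details that a protocol may leave to a later plan, and section 14 defers to one. Their absence is not a fault. No significance test is stated, so the power figures illustrate the limits of a small sample and do not describe a rule in the protocol. Both points stand.

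A reader might infer that a real difference would probably be missed. The documents do not support this: it depends on a subset size, an SD and a true difference that are not given. It holds for differences of about 0.5 SD with 30 or fewer per arm, but a difference of 0.8 SD is more likely found than missed from about 15 per arm.

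A reader might also infer that delivery cost is left out or set equal between arms. The section does not say so. Its list of resource items is open-ended, and the general sensitivity analyses could vary delivery time. All that can be said is that no route into the costs is stated and that the validation-only wording points away from one.

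Nor is a bias towards cost-neutrality shown. The sign of any delivery difference is unknown, it could offset or add to other cost differences, and nothing in the documents allows its size in pounds to be judged.

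**Conclusion.** The point holds as a fault of wording and method in one sentence of section 17. A small subset cannot confirm that delivery is unrelated to the drug, and restricting the times to that purpose leaves an observed difference without a stated place in an analysis whose aim is cost-neutrality. Under the assumed sizes, a difference of 0.5 SD could well go unseen (power 34% at 20 per arm, 48% at 30), while large differences would probably show. Whether a missed difference would change the economic conclusion cannot be determined from the documents. The consequence is confined to one cost component of a secondary outcome. The primary non-inferiority analysis is unaffected.

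**What to change.** In section 17, replace the validation-only sentence with wording to this effect:

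> The between-arm difference in length of consultation for delivery will be estimated and reported with its 95% CI. This difference, valued at staff unit cost, and its confidence limits will be carried into the cost comparison as a named sensitivity analysis.

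Add one sentence stating whether preparation out of the participant's sight is included in the recorded time, since that is a step at which the two drugs are known to differ.

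The estimate uses consultation times that are already to be collected. Neither an equivalence margin nor a larger subset is required, because the interval carries the uncertainty through. If preparation is to be included and is not already timed, a defined start point or a separate timing would be needed, which is a small extra burden. The main downside is that a wide interval may make the economic conclusion less clear-cut.
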